CT	Computed Tomography
DIAL	Duke Image Analysis Laboratory
DSMC	Data Safety and Monitoring Committee
DUMC	Duke University Medical Center
FDA	Food and Drug Administration
GCP	Good Clinical Practice
GOLD	Global Obstructive Lung Disease
ICH	International Conference on Harmonization
IRB	Institutional Review Board
MRI	Magnetic Resonance Imaging
PFP	Perfluoropropane gas
PFT	Pulmonary Function Test
SF6	Sulfur Hexafluoride
SQUID	Scalable Query Utility and Image Database

1 Background

1.1 *Investigational Agent*

Perfluoropropane gas (PFP or C₃F₈) (Air Liquide, DMF #16400)

1.2 *Preclinical Data*

Various laboratories around the world have successfully used PFx gas mixtures to image morphology and function in animal lungs in vivo and in ex-vivo human lungs. Likely the first use of PFx gases in an animal study was in 1984 (20) where perfluoromethane mixed with oxygen was compared to Xenon ventilation CT studies in dogs. There was little additional activity in the field until 1998 when Kuethe's group demonstrated the use of perfluoroethane mixed with oxygen to image rat lungs using 19F MRI and respiratory triggered imaging (13). Two years later Schreiber's group demonstrated 'breath-hold' imaging of the lungs of ventilated pigs using SF6 and 'ultrafast' MRI (24). The same group evaluated dynamic imaging including wash-in/washout kinetics of pulmonary ventilation in 2001, again in ventilated pigs (23). Kauczor reviewed various strategies for lung ventilation assessment using MRI in 2002 and cited six animal studies using PFx gases for such purposes (11). Jacob et al. demonstrated imaging of ventilation and diffusion in diseased and healthy excised human lungs as well as in 7 excised canine lungs using perfluoroethane (9). Perez-Sanchez et al. used SF6 to create diffusion-weighted images in anesthetized rats as well as calculated apparent diffusion constant (ADC) maps in 2005 (18). The same group demonstrated the impact of pressure and air-SF6 composition on ADC maps in rats in 2005 (21). Schreiber's group demonstrated sub-second SF6 images in pigs in 2006 as well as static 3D and dynamic wash-in images (26). Conradi et al. expanded on previous work and evaluated hyperpolarized 3He in humans as well as PFx gases in excised healthy and emphysematous human lung using perfluoroethane and perfluoropropane (4). Most recently Schreiber's group has compared MRI of inhaled SF6 with respiratory gas analysis in anesthetized pigs and found correlations adequate for lung function analysis (22).

1.3 *Risk/Benefits*

There likely will be no direct benefits to the subjects, other than increased understanding of their COPD. There will be not direct benefits to the subjects without lung disease. The benefits resulting from this research includes a better understanding of COPD structure/function relationships and how these relate to clinical trajectories and therapeutic responses. This should translate into better-targeted therapies and more focused clinical trial designs.

1.3.1 *Potential Risks*

1. Pain and/or hematoma formation may occur at blood sampling site. This is not a serious complication.
2. Dizziness during blood sampling may occur.
3. Spirometry may exacerbate bronchospasm, but in our laboratory this has not been a

This document contains confidential information belonging to Duke. Except as otherwise agreed to in writing, by accepting or reviewing this document, you agree to hold this information in confidence and not to disclose it to others (except where required by applicable law) or to use it for unauthorized purposes. In the event of any actual or suspected breach of this obligation, Duke should be promptly notified.

serious problem.

4. Ionizing radiation exposure from HRCT
5. The risks of participating in the MRI component of the study are considered minimal. MRI is a non-invasive imaging modality that involves no ionizing radiation. At the time of recruitment/consenting and again before the MRI session, all subjects will complete a standard questionnaire to screen for contraindications to MRI imaging (e.g. presence of metal in the eye).
6. The primary risk of the perfluorinated gases would be asphyxiation if breathed without oxygen present. This risk is minimized by obtaining the medical grade agents premixed with oxygen and with certificates of analysis. Further, as described in the preliminary data and research methods the source gas oxygen level is tested in the source gasbag prior to the study (510k cleared Oxygraf system) and the subject's oxygen saturation is monitored with pulse oximetry before, during and after the MRI. Any abnormal drop in oxygen saturation based on absolute levels ($\text{SpO}_2 < 90\%$) or levels observed relative to room air breath-hold maneuvers OR any indication of a problem will cause termination of the procedure. In addition, the gas is delivered via a disposable mask with spirometer filters to isolate the subject from the gas delivery system. Further, we monitor inhaled and exhaled flow with MR compatible pneumotachometers (510k cleared).

1.3.2 Protection Against Risk

1. Pain and/or hematoma formation may occur at the blood drawing site. We have experienced coordinators and pulmonary function technologists certified in both arterial and venous blood sampling.
2. Dizziness during blood sampling may occur. Subjects will be supine during blood sampling to avoid this problem.
3. Spirometry may exacerbate bronchospasm, but in our laboratory this has not been a serious problem.
4. Subjects will stay on their prescribed oxygen levels while participating in the study. Please note, this includes all the imaging components (CT and MRI)
5. HRCT will be performed in accordance with all Duke Department of Radiology procedures to minimize unnecessary ionizing radiation. The risks of the delivered radiation (increased cancer risk) is described out in the required consent language and compared to other risks of everyday life (refer to section 1.3.4).
6. All data will be maintained in secured files within the Duke Research site or in the SQUID research image management system.
7. Subjects will be monitored as follows during the imaging procedures: (a) monitoring of SpO_2 before during and after the examination (any SpO_2 levels $< 90\%$ will cause the study to be terminated) (b) monitoring of exhaled oxygen (%) and CO₂ (%) using a laser based capnograph. Further, we monitor inhaled and exhaled flow with MR compatible pneumotachometers (510k cleared).
8. Duke University has formal education and certification procedures regarding research ethics (www.irb.mc.duke.edu/certification.htm). All research personnel will complete these in full before entry into the protocol; the nature and risks of the study will be reviewed with each subject.
9. Each subject will be given the opportunity to read the consent form and ask questions.

After all questions by the study subject are answered, and before any protocol specified procedures are initiated, each subject will sign and date the consent form. A copy of the signed consent will be provided to the subject

1.3.3 MRI Risk

MRI uses a magnet and radio waves to make diagnostic medical images of the body. There have been no ill effects reported from exposure to the magnetism or radio waves used in this test. However, it is possible that harmful effects could be recognized in the future. A known risk is that the magnet could attract certain kinds of metal. Therefore, The technologist will carefully ask the subject about metal within the subject's body (this includes certain dyes found in tattoos). If there is any question about potentially hazardous metal within the subject's body, we will be excluding the subject from participation in this research study. We will also keep the exam room locked so that no one carrying metal objects can enter while the subject is in the scanner.

The study involves entering a large room in which a magnet is present. The subject will be placed on a narrow bed and then slid into a small tunnel approximately 6 feet in length and 25 inches in diameter. The subject will be asked to lie still for about one hour on this bed. The subject will hear a loud machine-like noise. The subject may be asked to have a harmless monitoring device applied during the study. During the study, the subject can have voice contact and physical contact with someone in attendance if you desire.

1.3.4 Computed Tomography (CT)

CT is a way to make x-ray images of the inside of the body. The CT scanner is a doughnut-shaped machine that uses x-rays to create computer pictures that show structures inside your body more clearly than regular x-ray pictures. During the procedure, a technologist will take the subject into the CT scan room where the subject will lie down on the table (usually on the subject's back) inside of the CT machine. The subject should get comfortable because it is very important the subject does not move during certain parts of the test. CT examinations differ depending on the part of your body being studied. For example, if your abdomen is being studied, a series of pictures will be taken from your lower chest to your lower pelvis. During the study, the subject will be asked to hold their breath so that the pictures will not be blurred. The machine will make some noise, and the table will move during the scan. Also, the subject may receive signals from the technologist or from the machine about their breathing.

If the subject is taking part in this research, the subject will have one or more medical imaging studies that use radiation. The tests or treatments the subject will have include lung CT scan (inhale/exhale). The radiation dose from this research is about 4 millisievert. To give subject an idea about how much radiation will get, we will make a comparison with an every-day situation. Everyone receives a small amount of unavoidable radiation each year. Some of this radiation comes from space and some from naturally occurring radioactive forms of water and minerals. This research gives your body the equivalent of about 1 extra year's worth of this natural radiation. The radiation dose we have discussed is what you will receive from this study only, and does not include any exposure you may have received or will receive from other tests.

A possible health problem seen with radiation exposure is the development of cancer later in life. This extra cancer risk is higher at younger ages and for girls and women. The extra lifetime risk of dying of a fatal cancer due to the radiation exposure from this research may range from about one in 8,000 to about one in 3,000. At such low radiation exposures, scientists disagree about the amount of risk. These estimates are very uncertain, and there may be no extra risk at all.

We can compare this possible extra cancer risk to other risks (over a lifetime) that everyone is subject to in everyday life. For example, the chances of a person dying of cancer with no extra radiation exposure are about one in 4. The chances of dying in a car crash are about one in 82, and the chances of being killed by a car while crossing the street are about one in 730.

1.4 Dose Rationale

Each subject will receive PFP as a contrast agent to visualize the airway and alveolar spaces in their lungs using magnetic resonance imaging of inert gas/oxygen mixtures.

1.5 Trial Design

An open label study in 250 subjects over five years. We are planning 130 subjects with COPD (varies stages of GOLD I-IV) and 120 normal subjects (non-smokers, ex smokers and current smokers with normal PFT's).

1.6 Literature

Gas trapping by HRCT

Air trapping can be detected by CT (14) (11) at suspended or full expiration with straightforward analysis of the image density in the lung field usually by counting pixels below a threshold value, e.g. <-856 in the COPDGene protocol. Air trapping using HRCT has been shown in recent work associated with the COPDGene project to be perhaps the only clinical phenotype to identify the several genotypes of COPD (<http://www.copdgene.org/ats-abstracts-2010>) (17) (7). We will focus on measuring such trapping in Aim 1.1 as well as washout using temporal measures of PFx image intensity in Aim 1.

Preliminary Studies

1. IND and Mixed Gases from Air Liquide/Scott Medical Products

Before the initiation of these studies we received a full FDA safety review and obtained IND 104,917 (Evaluation of Regional Ventilation in Normal Subjects and Subjects with Airway and Lung Disorders Using 19F Magnetic Resonance Imaging of Inert Perfluorinated Gases mixed with Oxygen (SF6, and PFP): A Phase 1 Study). We provided this information to our IRB in support of local approval of the protocol. Our shipments of gas mixtures have undergone microbial limit testing under USP <1111>, USP <61> and USP <62> as required by the FDA. Note that these gases are supplied at low pressure to insure that the dense gas component remains in the gaseous state. Example calculations follow: The gas mixture is formulated to have a 'dew point' of 0°C, i.e. it will not 'condense' above 0°C. The vapor pressure of PFP at 0°C is 60.41 psi. In order to determine the overall pressure of the mixture we divide the vapor pressure by the concentration in the mix to get the corresponding mix pressure (at 0°C). Then multiply by 294/273 (°Kelvin to °C conversion) to find the pressure at 21°C/70°F (assumed room temperature). So, for 79% PFP mix, it is: $60.41 / 0.79 = 76.46$ psia @ 0°C $\times 294/273 = 82.35$

psia @ 21°C - 14.7 = 67.65 psig @ 21C.

2. Initial Human Images and Physiological Monitoring

We have initiated a proof of concept study under IND 104,917 and with local IRB approval (Evaluation of Regional Ventilation in Normal Subjects and Subjects with Airway and Lung Disorders Using 19F Magnetic Resonance Imaging of Inert Perfluorinated Gases mixed with Oxygen (PFP): A Phase 1 Study). We have consented 44 subjects minus one withdrawal, screened 43 subjects in the study with the characteristics described in Table 1 and scanned 30 subjects (reasons for non scanning of subjects: 1 voluntary withdrawal prior to any study participation, 5 body habitus (too obese), 4 screen fails, 4 MRI contraindications).

Disease Status	Number of Subjects Screened (F/M)
Normal	13 (5/8)
COPD	11(7/4)
COPD, Emphysema	4 (1/3)
COPD Emphysema, Asthma, Small Airway Disease	1(1/0)
COPD Asthma, Small Airway Disease	1 (1/0)
Asthma	2 (2/0)
Asthma, small airway Disease	2 (2/0)
Cystic Fibrosis	5 (4/1)* all with lung transplant
Lung Transplant	2 (1/1)
Small Airway Disease	1 (1/0)
Unknown Etiology	1 (0/1)
Total	43 (25/18)

Table 1: Disease profiles of screened subjects in the phase 1 proof of concept study

2 Trial Objectives

The proposed study will determine regional qualitative and quantitative lung function information in the context of the clinical trajectory of COPD defined by the cross sectional cohort components. Due to the long time-frame of this disease we are using a modified case control design that allows a cross-sectional evaluation of the proposed measures in aims 1-2 to identify putative markers that could later be tested as prognostic factors in longitudinal studies. In the case of these PFx/oxygen mixtures, the availability of multi-liter quantities allows for wash-in/wash-out image acquisition and analysis allowing direct measures of gas trapping in a manner not easily achieved with any existing modality.

3 Trial Design

The central hypothesis and current observation is that PFx gases used as contrast agents provide functional images of the lung airways including important regional ventilation information such as ventilation defect severity and gas trapping. We will test the central hypothesis and accomplish the overall objective by addressing the following specific aims:

3.1 Primary Study Aims/Secondary Aims

Aim 1: Determine quantitative measures of lung ventilation performance in terms of direct measures of gas trapping measured during washout of the perfluorinated gas mixture.

Sub-aim 1.1: Compare gas trapping from aim 1 with air trapping by HRCT using conventional analysis procedures.

Sub-aim 1.2: We will accomplish this aim (as well as Aim 2) in a well-characterized cohort of subjects with COPD and subjects with normal global pulmonary function tests (non-, ex- and current smokers). This cohort will provide the basis for the cross sectional evaluation of the imaging markers in all aims with respect to disease severity (e.g. GOLD status) and risk factors (e.g. smoking)

Aim 2: Determine ventilation defect severity by comparing regional gas signal during wash-in of the perfluorinated gas mixture to steady state in the same cohort.

The outcomes of the work proposed in the aims is expected to demonstrate a novel quantitative approach for ventilation defect and gas trapping evaluation of regional lung function in humans that would be easily deployed for multi-center studies. It should also provide a set of biomarkers that could better inform evaluation of new treatments.

3.2 Trial Treatment

Each subject will receive PFP gas as a contrast agent to visualize the airway and alveolar spaces in their lungs using magnetic resonance imaging of inert gas/oxygen mixtures. The subjects will receive the gas by breathing normoxic mixtures of the gas using a 6500 V2 Disposable oral-nasal mask and a standard Douglas Bag system. No additional drug products, investigational or otherwise will be provided in this study. The subject will be monitored with a MRI compatible pulse oximeter as well as exhaled % oxygen and carbon dioxide.

3.3 Duration

3.3.1 Screening (V0)

1. Obtaining Informed Consent from each subject
2. History and Physical exam. The history will focus on onset of symptoms, co-morbidities, and smoking/occupational/environmental history. Also included:
 - a. An assessment of patterns of exacerbations (mild = use of oral antibiotics and/or steroids for an acute change in respiratory status; moderate = hospital admission for a change in respiratory status; severe = requirement for mechanical ventilation for a change in respiratory status).
 - b. A measurement of the body mass index (BMI).
 - c. A medication history (oral steroids, chronic bronchodilator use, oxygen use) with an emphasis on whether adherence was adequate.
 - d. Assessment of gastro-esophageal reflux disease (10)
 - e. Epworth Sleepiness Scale as a marker of sleep disordered breathing

- f. Estimate of daily physical activity (25)
- 3. Pulmonary function tests will include spirometry, plethysmographic lung volumes, and corrected carbon monoxide diffusing capacity (DLCO). All procedures will be done in accordance with ATS/ERS standards (3) (15) (17).
- 4. High resolution computerized scans of the chest (HRCT). Emphysema scores will be calculated per COPD Gene protocol (7). We will also explore novel approaches to quantifying airway structures (5) (16)
- 5. A six-minute walk test with monitoring of pulse oximetry and heart rate will be conducted in accordance with ATS standards (1)
- 6. Vital Signs will be measured and recorded (temperature, heart rate, blood pressure and respiratory rate)
- 7. Pulse oximetry will be measured and recorded.
- 8. Weight and height will be recorded.
- 9. Quality of Life (QOL) will be assessed using the St George self-administered instrument
- 10. A serum pregnancy test will also be performed in women with child bearing potential.

MRI will be collected at the study visit 1 after the screening visit. Where possible the screening visit (V0) and MRI visit (V1) will be accomplished on the same day for the convenience of the subject. In all cases, the MRI will be followed-up immediately following the MRI procedure for any adverse events. Finally, all subjects will be contacted 24 hours post-MRI by phone for follow-up regarding any adverse events.

3.3.2 Visit 1: MRI

Visit 1 will include a rescreening for MRI safety by the MR Technologist, (if not performed at screening), the MRI exam, Vital signs (temperature, heart rate, blood pressure, respiratory rate and pulse oximetry) will be collected at pre and post imaging examination. A urine pregnancy test will be performed on female of child-bearing potential if the screening serum test was given 48 or more hours earlier. They must have a negative result to further participate in the study.

Additionally, subjects will be carefully observed for any signs of hypoxia before, during, and after the MRI exam using pulse oximetry. Any SpO₂ reading < 90% will result in termination of the study.

Subjects will stay on their prescribed oxygen treatment, while participating in the study. Please note, this includes both imaging components (CT and MRI)

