3.3.3 Twenty-four Hour Follow-up

Twenty-four hours post V1 (and subsequent imaging visits) the subjects will be contacted by phone and questioned regarding any post MRI adverse events. (Refer to Table 2 for the scheduled of events.)

Table 2: Scheduled of Events

Protocol Activities	Screening (V0)	Study Visit (V1)	Follow Up (24 hours by phone)
Informed Consent	X		
General Medical History	X		
Physical Exam	X		
HRCT ¹	X		
Weight and Height	X		
Concomitant Medication	X		
Pregnancy Test (serum and urine) ²	X		
Quality of Life Assessment	X		
MRI Screening Form	X	X	
Vital Signs Assessment	X	X	
Pulse oximetry	X	X	
Six Minute Walk Test	X		
Thermally Polarized Gas MRI			X
Pulmonary Function Test	X		
Adverse Event Assessment		X	X
¹ depending on scheduling, the HRCT will be performed at screening (V0) or between screening (V0) – study visit (V1)			
² Females of child-bearing potential who had a blood pregnancy tests performed, will have a urine pregnancy test if blood test was given 48 or more hours earlier			

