3.5 Data Identification

According to ICH and FDA guidance, the following data will be considered source and will be recorded directly into each subject's CRFs.

- Screening (V0)
 - Informed Consent date
 - General Medical History
 - Physical Exam
 - Weight/Height
 - Concomitant Medications
 - Quality of Life Assessment
 - Vital Signs
 - Pulse Oximetry
 - 6 Minutes Walk
 - PFT First section
- Study Visit (V1)
 - Vital Signs (pre and post imaging)
 - Pulse Oximetry (pre and post imaging)
 - For Women of child bearing potential
 - Date of the results of the pregnancy test
 - Adverse Events (post imaging)
- 24hr Follow up phone call
 - Adverse Event
 - Follow-up

The following data will be considered source but will not be recorded directly into each subject's CRFs. This data will likely be found in the subject's research folder (paper) and/or electric medical record.

- Informed Consent
- For Women of child bearing potential
 - Result of pregnancy test
- MRI screening Form
- HRCT reading
- PFT Testing results

The CRFs, the MR/HRCT images and PFT testing results will serve as source documents for this study.

4 Selection of Subjects and Withdrawal/Discontinuation

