4.1 Inclusion/Exclusion Criteria for Subjects with COPD

Inclusion criteria

Subjects must meet all of the following inclusion criteria to be eligible for enrollment into the

trial

1. Outpatients of either gender, age > 18.
2. Willing and able to give informed consent and adhere to visit/protocol schedules.
(Consent must be given before any study procedures are performed.)
3. Women of childbearing potential must have a negative serum pregnancy test. This will be confirmed before participation in this investigational protocol.
4. Clinical diagnosis of COPD confirmed by Spirometry demonstrating FEV1/FVC <0.70.

Exclusion criteria

Subjects presenting with any of the following will not be included in the trial:

1. Abuse of alcohol or illicit substances.
2. Medical conditions, which, in the opinion of the investigator, will significantly affect five-year survival.
3. Medical or psychological conditions which, in the opinion of the investigator, might create undue risk to the subject or interfere with the subject's ability to comply with the protocol requirements.
4. Conditions that will prohibit MRI scanning (metal in eye, claustrophobia, inability to lie supine, renal insufficiency with eGFR < 60 mL/min/1.73 m²)

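### A delayed HRCT can come before the 48-hour pregnancy retest, which the text places only at the MRI visit

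*Combined protocol and SAP*

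**What the plan says.** The serum pregnancy test belongs to screening (section 3.3.1, item 10), and both cohorts need a negative result to enter. Section 4.1 puts it as "Women of childbearing potential must have a negative serum pregnancy test", and section 4.2 has the same criterion.

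The retest appears under the MRI visit, in section 3.3.2: "A urine pregnancy test will be performed on female of child-bearing potential if the screening serum test was given 48 or more hours earlier". The same section makes a negative result a condition of continuing. Section 3.5 lists "Date of the results of the pregnancy test" under V1.

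Table 2 (section 3.3.3) has two relevant footnotes. On CT timing, footnote 1 reads "depending on scheduling, the HRCT will be performed at screening (V0) or between screening (V0) – study visit (V1". On the retest, footnote 2 says that these women "will have a urine pregnancy test if blood test was given 48 or more hours earlier", and names neither a visit nor a procedure.

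On the interval between visits, section 3.3.1 says only: "Where possible the screening visit (V0) and MRI visit (V1) will be accomplished on the same day". No maximum is given. Section 1.3.1 names "Ionizing radiation exposure from HRCT" among the risks and notes that MRI involves no ionising radiation. Section 1.3.4 puts the dose at about 4 mSv.

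**The concern.** By requiring a second test once the serum result is 48 hours old, the protocol sets its own limit on how long that result stands alone. The text applies this limit at V1, before the MRI and the gas inhalation. The HRCT may be done on an earlier day, and nothing clearly applies the limit there.

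What is at stake is subject safety. If the schedule is followed as written, a pregnancy that the earlier serum test did not show could come to light only after the CT. Both cohorts admit adults over 18 with no upper age limit, so women of child-bearing potential are eligible, including among the 120 planned normal subjects. Sample size, power and analysis are not touched.

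**Working it through.** The plan states no figure to reproduce. The check is one of timing, followed by a rough illustration of numbers.

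**Timing.** Let the serum test be at hour 0, the HRCT at hour *h* and V1 at hour *v*, with 0 ≤ *h* ≤ *v*. Footnote 1 permits any such *h*, and no section caps *v*.

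| Case | Retest at V1? | Age of serum result at HRCT |
|---|---|---|
| *v* < 48 (includes same-day visits) | not required | under 48 h |
| *h* < 48 ≤ *v* | required, after the HRCT | under 48 h |
| 48 ≤ *h* < *v* | required, after the HRCT | 48 h or more |

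Only the third case is a gap. Example: serum test on day 0, HRCT on day 5, V1 on day 7. Each step is allowed. The CT is done on a 5-day-old result, and the retest follows 7 − 5 = 2 days later.

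**Could another provision close the third case?**

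- Sections 4.1 and 4.2 require a negative serum test but give it no validity period and do not tie it to the HRCT.
- Sections 1.3.2, 1.3.4 and 4.4.2, which deal with CT, mention no pregnancy test.
- In Table 2 the pregnancy-test row is marked under V0. The column marks are not decisive: as the table reads here, the gas MRI is marked under the phone follow-up, which may be a fault in reading the PDF. Even a correct V0 mark would not tie a retest to a later HRCT.

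**Illustration of numbers (not a protocol figure).** The inputs are the phase 1 disease table (Table 1, under the preliminary studies in section 1.6) and the planned group sizes (section 1.5).

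- Women among normal subjects: 5/13. Planned 120, so 120 × 5/13 = 46.2.
- Women among subjects with COPD: (7+1+1+1)/(11+4+1+1) = 10/17. Planned 130, so 130 × 10/17 = 76.5.
- Total: 46.2 + 76.5 ≈ 123 of 250, if the phase 1 sex mix carries over.
- Assumed share of these who are of child-bearing potential and have the HRCT 48 hours or more after the serum test: 1% to 10%. The documents give no figure.
- Result: 122.6 × 0.01 = 1.2 to 122.6 × 0.10 = 12.3, or about 1 to 12 women.

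This range counts women with a late HRCT, not exposed pregnancies, which would be fewer.

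**The case against.** The strongest reply is that this is a residual case. Every woman of child-bearing potential has a negative serum test at entry, the HRCT is itself a screening item, and same-day visits are preferred. The gap needs split visits, an HRCT not done at V0 and a delay of at least 48 hours; harm further needs a pregnancy that the serum test missed or that began later. All of this stands, and it limits the size of the problem. It does not remove the permitted sequence.

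Second, footnote 2 is not limited to V1 and could be read as covering the HRCT. That reading is possible, but the footnote does not state it, and the one section that gives the retest a visit puts it at V1.

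Third, section 3.5 is weak support for confining the retest to V1. It lists where data are recorded and does not say whether the date is that of the serum or the urine test. That is fair; the point rests on section 3.3.2 and the two footnotes.

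Fourth, section 1.3.2 says "HRCT will be performed in accordance with all Duke Department of Radiology procedures to minimize unnecessary ionizing radiation", and those procedures may include a pregnancy check. Their content is not shown, so the gap is established for the visible text only.

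Fifth, the 1% to 10% share is an assumption, the sex mix comes from 13 and 17 subjects of another study, and the true count could be zero. This is correct, and the conclusion does not depend on the count.

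Finally, nothing in the documents sets 48 hours as a standard for CT. That is true; the proposal extends the protocol's own limit to the procedure that carries the radiation.

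**Conclusion.** The concern holds. The schedule as written allows an HRCT to precede the retest, on a serum result at least 48 hours old, and no visible provision rules this out. The retest at V1 is not misplaced, since it precedes the MRI and gas inhalation; the HRCT is simply not clearly covered.

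The exposure is about 4 mSv to the subject; the dose to a fetus is not given. The number of women is unknown and probably small. The conclusion assumes that some subjects have split visits with a late HRCT and that the unseen radiology procedures do not already require a test. The change should be made because it is cheap and protects subjects, not because the trial's results are at risk.

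**What to change.** Keep the retest before the MRI and gas inhalation. Add one sentence to section 3.3.2, for example: *Women of child-bearing potential must have a negative pregnancy test within 48 hours before the HRCT and within 48 hours before the MRI; if the serum test is older than this at either procedure, a urine test is done first.* In Table 2, footnote 2, add that the 48 hours run to each imaging procedure.

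The cost is one sentence and a few words. In practice it means one earlier or repeated urine test, of a kind already in the protocol, for the few women whose HRCT is delayed.
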